9.7 Analysis of Exploratory Endpoints

Limited exploratory endpoints will be analyzed analogously to primary and secondary endpoints with the same strategies for ICEs.

Binary endpoints in Period 1 will be analyzed with a stratified test of risk difference and continuous endpoints will be analyzed with an MMRM model in general. Risk differences, differences in LSMeans, and p-values will be calculated for time-points in Period 2, but will be used for descriptive purposes only.

Continuous data at timepoints before and including the primary timepoint will use all data from planned assessments up to and including the primary timepoint; continuous data after the primary timepoint will use all data from all planned assessments. Baseline parameter value, Stratification variables, visit week, treatment group and interaction of treatment and visit week will be included in the MMRM model.

Analyses of binary endpoints in Period 1 or Period 1 + Period 2 will use the full FAS as the analysis set. Analyses of binary endpoints of Period 2 data only will use the subjects in FAS who have at least one dose of treatment in Period 2.

Results for continuous endpoints will presented as LS mean changes and associated SEs with associated 95% CI and p-values. Exploratory endpoint results will also be listed.

The following binary endpoints will be analyzed analogously to the primary endpoint of HiSCR75 at Week 12:

- HiSCR50, HiSCR75, HiSCR90 and HiSCR100 at Weeks 2, 4, 8, 16, 24, and 32;
- AN count of 0, 1, or 2 at Weeks 4, 8, 16, 24, and 32 among subjects with baseline Hurley Stage II;

- Proportion with at least 3 points reduction from baseline in NRS in Patient Global Assessment of Skin Pain at its worst, among subjects with baseline NRS ≥ 4 , at weeks 4, 8, 16, 24, and 32. NRI will be handled analogously to the corresponding secondary endpoint analysis.
- HS flares through Weeks 4, 16, and 52;

The binary endpoints listed above (excluding Flares) at the Week 24, 32, and/or Week 52 timepoint will also be analyzed for just the subgroup of FAS who had at least one dose of study drug in Period 2. The ICE handling strategy corresponding to NRI due to antibiotic use will be slightly modified for the analyses of responder rates corresponding to Period 2 visits: subjects originally randomized to placebo treatment and who receive antibiotic therapy that could affect HS *after the first dose of study treatment in Period 2* will be included in the analysis by imputing as non-responders (non-response imputation or NRI) at subsequent timepoints. If these subjects took antibiotics that could affect HS *prior to the first dose of study treatment in Period 2*, they will not be automatically assigned as non-responders unless the forbidden antibiotic was taken in Period 2.

The following continuous endpoint will be analyzed with an MMRM model. LS mean changes and associated SEs with associated 95% CI and p-values will be presented. For time-points on or before Week 16, the model will include only data up to Week 16. For time-points after Week 16, the model will include all available time-points. Mean values, mean changes and associated descriptive statistics along with 95% CI (for change from baseline) according to the treatment group:

- Change from baseline in DLQI at Weeks 4, 8, 16, and 24;

All other exploratory endpoints will not be summarized for the purposes of the abbreviated CSR.

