9.5 Analysis of Primary Efficacy Endpoint

The primary efficacy variable is defined as HiSCR75 at Week 12.

The statistical null and alternative hypotheses to be used to assess the primary objective are:

$$H_0: \pi_{ABY} - \pi_{PBO} = 0$$

$$H_A: \pi_{ABY} - \pi_{PBO} \neq 0$$

where π_{ABY} and π_{PBO} are the proportion of subjects achieving HiSCR75 at Week 12 among subjects randomly assigned to receive izokibep and placebo, respectively.

The treatment policy strategy approach for the estimand will be used in general, so subjects will be included using observed data at Week 12 regardless of treatment compliance, use of rescue medications or procedures except as noted below, or any other protocol deviations.

Subjects who receive antibiotic therapy that could affect HS will be included in the primary analysis by imputing as non-responders (non-response imputation or NRI) at subsequent timepoints. A list of all oral antibiotic therapy that results in such imputation will be finalized after review of all oral antibiotic therapy received by any subject and before unblinding of the study, and will include tetracycline, clindamycin, and possibly other products. Similarly, subjects with missing HiSCR75 assessments at Week 12 due to discontinuing treatment due to an AE or lack of efficacy will also be imputed as NRI. These subjects will be identified by meeting any of the following criteria:

- Subject has adverse event with action taken = “Drug Withdrawn” and corresponding AE start date is before study day 84 and last dose of study drug is taken before study day 84 or
- Subject has last dose of study drug taken before study day 84 and reason for discontinuation of treatment is any of the following:
 - Adverse event
 - Death
 - Lack of efficacy
 - Disease progression

Other subjects with missing data will have efficacy data imputed using multiple imputation, as follows:

Multiple imputation will be implemented to replace missing endpoint data using multiple draws from a posterior predictive distribution estimated from the placebo group only. First, a monotone missingness pattern will be enforced using Markov Chain Monte Carlo (MCMC). The MCMC process will use predictor variables of:

- baseline abscess count (continuous)
- baseline inflammatory nodule count (continuous)
- baseline draining fistula count (continuous)
- age (continuous)
- baseline BMI (continuous)

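### Period 2 risk differences and p-values for HiSCR and AN count 0 to 2 use a different antibiotic non-response rule in each arm, which can only shift them against continuous izokibep or leave them unchanged

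*SAP*

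**What the plan says.** The default rule is in SAP 9.5: "Subjects who receive antibiotic therapy that could affect HS will be included in the primary analysis by imputing as non-responders" at later timepoints. It has no expiry and does not depend on arm; SAP 6.7.1.4 states the same rule. SAP 9.7 carries it over: "Limited exploratory endpoints will be analyzed analogously to primary and secondary endpoints with the same strategies for ICEs". Protocol 9.3.4 makes the same commitment.

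SAP 9.7 then says that the antibiotic handling "will be slightly modified for the analyses of responder rates corresponding to Period 2 visits". The group named is "subjects originally randomized to placebo treatment and who receive antibiotic therapy that could affect HS" after their first Period 2 dose; they become non-responders from that point. If their use came before that dose, "they will not be automatically assigned as non-responders unless the forbidden antibiotic was taken in Period 2". Izokibep-randomised subjects are not mentioned, so the default rule still governs them. That last step is an inference, but the section offers no other rule for that arm.

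On between-arm results, SAP 9.7 says: "Risk differences, differences in LSMeans, and p-values will be calculated for time-points in Period 2, but will be used for descriptive purposes only". SAP 8.1 classes every summary after Week 16 as exploratory.

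**The concern.** A difference between randomised arms needs one definition of response. Suppose two subjects each take the same short clindamycin course at Week 3 (SAP 9.5 names clindamycin as a listed drug), do not repeat it, and have the same qualifying lesion counts at Week 32. The placebo-to-izokibep subject counts as a responder and the continuous-izokibep subject as a non-responder. Only the randomised arm separates them. At Week 32 one arm is judged on about 16 weeks of antibiotic use and the other on about 32; at Week 24, on about 8 and 24.

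At stake is how the longer-term results are read. The study stops at Week 32, so Weeks 24 and 32 are the main responder results after the switch. Part of any narrowing between switchers and continuous izokibep could come from the imputation rule.

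Little else in the plan would show this. SAP 9.5 tabulates non-response imputation with reasons at Week 12 only, SAP 9.5.1 drops the sensitivity analyses of the primary endpoint, and SAP Section 5 does not list this departure among the changes from the protocol.

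**Working it through.** **The plan's own figure.** The documents give no figure for Period 2. The only design figure is the Week 12 power in Protocol 9.5 and SAP 4.4: 15% versus 35%, 125 per arm, two-sided alpha 0.05, unstratified, about 95%. With pooled variance under the null, the standard errors are √(2 × 0.25 × 0.75 / 125) = 0.0548 and √((0.15 × 0.85 + 0.35 × 0.65) / 125) = 0.0533. Then (0.20 − 1.96 × 0.0548) / 0.0533 = 1.74, which gives 95.9%. The figure reproduces, and this point does not touch it.

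**Set-up for a Period 2 visit.** In the izokibep arm, let `aI` be the share of subjects whose listed antibiotic use was in Period 1 only. Let `uI` be the response rate they would have at the visit if the antibiotic rule did not apply, and `RI` the response rate in the rest of the arm. Define `aP`, `uP` and `RP` likewise for the placebo-randomised arm. Subjects with use in Period 2 are non-responders under every rule and sit inside `RI` and `RP`.

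Izokibep minus placebo is then:

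- Forgive both arms: [(1 − aI)RI + aI·uI] − [(1 − aP)RP + aP·uP]
- Forgive neither arm: (1 − aI)RI − (1 − aP)RP
- SAP 9.7: (1 − aI)RI − [(1 − aP)RP + aP·uP]

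Subtracting:

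- SAP 9.7 minus forgive-both = −aI·uI
- SAP 9.7 minus forgive-neither = −aP·uP

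Both are zero or negative, so the direction does not depend on the unknown rates.

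**Illustrative size.** The documents give neither antibiotic-use rates nor Period 2 response rates, so all of these are assumptions: equal use and equal true response in both arms, 40% response in other subjects, 125 per arm. One common rule gives a difference of 0. SAP 9.7 gives −a × u. The p-values are from an unstratified normal approximation and show only what the rule alone would produce.

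| Period-1-only use, a | Shift at u = 20% | Shift at u = 40% | p-values |
|---|---|---|---|
| 2% | −0.4 points | −0.8 points | 0.95, 0.90 |
| 5% | −1.0 | −2.0 | 0.87, 0.75 |
| 10% | −2.0 | −4.0 | 0.74, 0.51 |
| 20% | −4.0 | −8.0 | 0.50, 0.19 |
| 30% | −6.0 | −12.0 | 0.30, 0.04 |

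The 30% row is an extreme. It borrows the approximate cap on stable antibiotic use at entry and supposes that all such use counts and ends before the first Period 2 dose.

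**Unequal use.** Take aI = 5%, aP = 10%, u = 30% in both arms and 40% in other subjects.

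- Izokibep, forgiven: 0.95 × 0.40 + 0.05 × 0.30 = 39.5%; not forgiven: 0.95 × 0.40 = 38.0%
- Placebo-randomised, forgiven: 0.90 × 0.40 + 0.10 × 0.30 = 39.0%; not forgiven: 0.90 × 0.40 = 36.0%
- Forgive both: +0.5 points. Forgive neither: +2.0. SAP 9.7: 38.0 − 39.0 = −1.0.

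In this example the mixed rule reverses the sign that both common rules give.

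**The case against.** The best defence is that the rule is uniform on the izokibep clock: each arm is judged on antibiotic use since its first izokibep dose. That fits the exploratory objective after Week 16, which is to estimate izokibep efficacy and not to compare with placebo. Antibiotic use on placebo is not an intercurrent event on izokibep, whereas use on izokibep may be a treatment failure, and forgiving it would raise the continuous-izokibep rate. No between-arm estimand is defined for these visits, and the outputs are labelled descriptive.

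This stands for rates within each arm. It does not carry over to a contrast between randomised arms, which SAP 9.7 nevertheless calculates with p-values. The Period 2 subset already enters both arms at a common landmark, the first Period 2 dose, so a common lookback is available.

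The objection on size also stands in part. Only use confined to Period 1 matters. Protocol 6.8.4 requires a rescue regimen to stay stable for the rest of participation, so compliant rescue begun in Period 1 would continue into Period 2 and count in both arms. Protocol 6.8.2.5 and 6.8.3 restrict other antibiotics for HS. What mainly remains is short courses for other conditions (Protocol 6.8.2.4) if the drug is listed, deviations, and entry antibiotics stopped after Week 16. The SAP does not say whether entry antibiotics count; if they do, the effect could be much larger.

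Four stronger readings are tempting but unsupported:

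- **That the rule makes response on continuous izokibep appear to wane.** A subject with Period-1-only use before the Week 16 visit is already a non-responder at Week 16 under the default rule and stays one. The placebo-only reset changes nothing within the izokibep arm.
- **That all responder endpoints are affected.** SAP 9.7 excludes flares from these Period 2 analyses. The pain endpoint's rules in SAP 6.8.1 and 9.6.4 concern analgesics and discontinuation, with no antibiotic rule.
- **That the loss can be put at several points.** Assuming 5% to 15% use and 30% to 50% response would give 0.05 × 0.30 = 1.5 to 0.15 × 0.50 = 7.5 points, but the documents support none of those rates.
- **That confirmatory conclusions are at risk.** The Week 12 hierarchy is tested separately and does not use Period 2 data.

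**Conclusion.** The point holds for the between-arm risk differences and p-values for HiSCR and AN count 0 to 2 at Period 2 visits. For HiSCR at Week 24 there is a further uncertainty: SAP 9.7 lists it, while SAP Section 5 and 6.9 do not.

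The direction is certain given the inferred default rule for the izokibep arm: against continuous izokibep, or no change. The consequence is that switcher catch-up could be exaggerated; the rule cannot create an advantage for continuous izokibep. The shift relative to forgiving both arms is the share of izokibep subjects with Period-1-only use times the response rate they would otherwise have. That is about 0.4 to 4 points under the assumed 2% to 10% and 20% to 40%. The true size cannot be found from the documents, may be small, and is zero if no such subject would have responded.

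Severity is low, because the results are exploratory and descriptive. It is worth correcting because the correction is cheap.

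**What to change.** In SAP 9.7, keep the since-first-izokibep-dose rule for within-arm Period 2 rates if wanted, and say there that it differs by arm. For Period 2 risk differences and p-values, use one lookback in both arms: non-response only for listed antibiotics taken on or after the first Period 2 dose. Show the cumulative since-Day-1 version for both arms beside it. Alternatively, do not report between-arm risk differences and p-values from the asymmetric rule.

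The cost is one sentence, one extra flag and one extra table. The common Period 2 lookback does not count Period 1 antibiotic use in the izokibep arm; the cumulative version shows what that leaves out.

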9.8 Analysis of Safety Endpoints

9.8.1 Study Drug Exposure and Compliance

Subject exposure to treatment will be summarized by treatment group and overall for the SAF.

Number of doses, duration of treatment, and percent compliance will be summarized by treatment group and overall through Week 16 and, separately, through Week 52 with descriptive statistics (n, mean, SD, median, minimum, and maximum). Compliance categories will be summarized by treatment group and overall for Week 16 and Week 52 with the number and percentage of subjects in each category. For the analyses through Week 52, a separate summary will be done for period 2, and separately, for the total study exposure.

9.8.2 Adverse Events

The number and percentage of subjects with AEs as well as the number of events will be summarized by MedDRA-coded SOCs and PTs.

The following AE summaries occurring through Week 16 will be presented by treatment group and overall:

- Overall summary of TEAEs
- TEAEs by SOC and PT
- TEAEs by Cumulative Severity Category by SOC, and PT
- Related TEAEs by SOC and PT

- Related TEAEs by Cumulative Severity Category by SOC, and PT
- Serious TEAEs by SOC and PT
- Treatment-related Serious TEAEs by SOC and PT
- TEAEs of Special Interest by SOC and PT
- TEAEs leading to discontinuation by SOC and PT
- TEAEs Experienced by >= 5% Subjects in Izokibep Group by SOC and PT
- Summary of ISRs
 - Total Number of subjects having at least 1 ISR (including count of events)
 - Subjects and Event ISRs Count by severity in the following categories:
 - Grade 1 or above
 - Grade 2 or above
 - Grade 3 or above
 - Grade 4 or above
 - Summary of signs and symptoms (subject counts/percentages and count of events)
 - ISRs (Subjects) Count by Injection Visit (if 1 subject has an ISR corresponding to multiple visits, the subject is counted in both)

The AE summaries listed above will also be produced for Period 2 for subjects with at least one dose of study drug in Period 2 (SAFP2). These will also be presented for Period 1 + Period 2 (Total study) combined for the safety analysis set (SAF).

Within each summary, a subject will only be counted once within each SOC and PT.

Summaries by SOCs and PTs will be sorted by SOCs by descending order of total incidence and PTs within SOC by descending order of total incidence. Where PTs tie, PTs will be sorted alphabetically. Summaries by PTs only will be sorted by descending order of total incidence.

All AE data will be listed and AEs and TEAEs will be presented together. Treatment-emergence status as well as period will be indicated in the listing. The listing will present the relative start and stop day of the AE calculated relative to the first dose of treatment and will be presented for those subjects who received at least 1 dose of treatment. If the AE is “Ongoing” it will be indicated as such in the listing and the relative stop day will not be calculated. Only original dates will be presented in the listing even though the relative day may be based on an imputed date.

The following listings will be presented for the SAF:

- Listing of all AEs (flag will be included for TEAE and safety follow-up AE)
- Listing of Serious TEAEs
- Listing of AEs Leading to Discontinuation of Study Treatment
- Listing of AEs of Special Interest
- Listing of ISRs
- Listing of Deaths

9.8.3 Clinical Laboratory Assessments

Clinical lab data will not be summarized or listed for the purposes of abbreviated CSR.

9.8.3.1 Liver Function Tests

A summary table will present the count/proportion of subjects who meet each of the 6 criteria for consideration of potential DILI and subjects meeting Hy's Law at any time through Week 16, and, separately, for any time through Week 52. A similar summary table will be created for Period 2 only, for just the subjects in the SAF with at least one dose of study treatment in Period 2. Baseline results will not be included in the table; only post-baseline liver function test values are flagged.

Potential liver toxicity will be assessed by listing subjects who met potential drug induced liver injury (pDILI) criteria as described in the protocol and by summarizing subjects who met Hy's Law for the SAF.

For subjects who meet any of the 6 criteria for consideration of potential DILI and subjects being classified as meeting Hy's Law or not meeting Hy's Law, all LFT results at any time through Week 52 will be listed, sorted by subject and date. Listing will include subject, treatment assignment, ALT, AST, ALP, bilirubin and INR, along with specific criterion met for DILI as well as met/not met Hy's Law. Subjects who met the criteria prior to or at Week 16, and anytime in Period 2 will be flagged.

9.8.4 Electrocardiograms

ECGs results will not be summarized or listed for the purposes of abbreviated CSR.

9.8.5 Vital Signs

Vital signs will not be summarized or listed for the purposes of abbreviated CSR.

9.8.6 Physical Examination

Physical examination findings will not be summarized or listed for the purposes of abbreviated CSR.

9.8.7 Other Endpoints

No additional endpoint analyses are planned.

9.9 Pharmacokinetic Assessments

Pharmacokinetic data will be summarized for the safety analysis set by treatment group and scheduled visit, including N (number of non-missing data), N BLQ (for concentrations only), arithmetic mean, standard deviation (SD), arithmetic coefficient of variation (CV%), geometric mean, geometric CV%, median, minimum, and maximum. Only trough collections are planned, so no calculations of PK parameters (maximum concentration, area under the concentration curve, etc.) will be provided.

For the calculation of summary statistics, pre-dose concentrations that are below the limit of quantification (BLQ) will be treated as zero and post-dose concentrations that are BLQ will be treated as missing.

Pharmacokinetic data may be combined with data from other studies of izokibep for modeling. If this is done, details will be described in a separate document.

9.10 Anti-Drug Antibodies

Samples tested for ADAs will be reported as positive or negative based on a confirmatory assay. Any continuous values of concentration (titers) will be summarized using observed data.

Subjects will be summarized at each scheduled visit according to the confirmatory test, with number (%) positive.

9.11 Subgroup Analyses

Subgroup analyses of the efficacy data will be not be done, due to the decision to write an abbreviated CSR.

10. COMPUTER SOFTWARE

Statistical analyses will be performed using SAS® version 9.4 or higher in a Windows environment, or R version 4.1.1 or later.

12. TABLE/FIGURE/LISTING SHELLS

The mock shells for the tables/figures/listings will be provided in a separate document.

13. APPENDICES

13.1 End Points Definitions and Scoring Method

13.1.2 Modified Sartorius Score

The modified Sartorius score includes an assessment of the anatomical regions involved, the numbers and scores of lesions for each region, the longest distance between 2 relevant regions (or size of a single lesion), and whether all lesions are separated by normal skin (yes or no). The detailed scoring is as following (Sartorius K, 2009):

Each region will score as defined in [Table 7](#):

Table 7: Scoring Modified Sartorius Score

Item No	Items	Scoring Rules	Points	Score:
1	Anatomical region	If the region is affected	3	
		If the region is not affected, the score for that region is 0, and no further calculations are needed for the region. If the region is affected, the following are added in addition to the 3 points for the region in line 1 above.		
	For each affected region:			
2	Nodules (Inflammatory)	Count from this region	1	$1 \times \text{count}$
3	Fistulae (Draining only)	Count from this region	6	$6 \times \text{count}$
4	Longest distance between 2 relevant lesions within a region or size of the lesion if single	< 5 cm	1	
		5 - 10 cm	3	
		> 10 cm	9	
5	Lesions separated by normal skin?*	Yes	0	
		No	9	
	Score for the region			Sum of above

* If Lesions separated by normal skin = "No" and/or Hurley Stage = "STAGE III" then 9 points is added for the region.

Score for each region is (if the region involved) = $3 + (\text{number of inflammatory nodule}) \times 1 + \{(\text{number of draining fistula}) \times 6 + \{0 < (\text{The longest distance between 2 relevant lesions [or size of lesion if single]}) < 5\} \times 1 + \{5 \leq (\text{The longest distance between 2 relevant lesions [or size of lesion if single]}) \leq 10\} \times 3 + \{(\text{The longest distance between 2 relevant lesions [or size of lesion if single]}) > 10\} \times 9 + (\text{all lesions separated by normal skin} = \text{Yes or Hurley Stage} = \text{"STAGE III"}) \times 9$

Modified Sartorius score is the sum of the score of each region. Any region with no involvement will have a score of zero for purposes of calculating the modified Sartorius score.

A region is considered “affected” if any of the following conditions are true:

- Abscess Count > 0 OR
- Any “Interventions needed DATE” question is not missing.
- Any “How many lesions had intervention” question > 0
- Non-draining fistula count > 0
- Draining fistula count > 0
- Non-inflammatory nodule count > 0
- Inflammatory nodule count > 0
- Hypertrophic scar > 0
- Longest distance > 0
- Normal appearance tissue = NO
- Hurley Stage contains “STAGE”

